Neurobiology of Alcohol and Nicotine Co-Addiction

[name], MD

NCT03338933

Table of Contents and Guide

Specific Aims and Rationale	1
Detailed Research Plan	2-3
Subject Recruitment/Inclusion	2-3
Detailed Analysis	4-8
Power	7-8
Risks and Protection from Risk	8-9
Participation of Non-Veterans	9
Data and Safety Monitoring Plans	10
Data Repository	10
Vulnerable Populations	10
Determining VA Research	10

2. Specific Aims: This proposal, ***Neurobiology of Alcohol and Nicotine Co-Addiction*** addresses the critical absence of information about the neurobiology of recovery from alcoholism in patients with co-existing alcohol use disorder (AUD) and nicotine use disorder (NUD). AUD and NUD (almost entirely cigarette smoking) are the most commonly abused (non-prescription) substances in the U.S. Co-addiction is particularly high in military veterans. For example, the Substance Abuse Treatment Program (SATP) at the Veterans Affairs Portland Health Care System (VAPORHCS) finds that 90% of veterans treated for AUD also meet criteria for NUD. Therefore, this Merit Review submission proposes to create a multidimensional quantitative model of alcohol and nicotine co-addiction (NAUD). **The purposes of this quantitative model are twofold:** (1) construct an integrative model which will add to the mechanistic understanding of the neurobiology of co-addiction by providing insight into the causal relationships among cerebral structure, function and behavior and (2) provide intermediate phenotypes or biomarkers in order to predict relapse or recovery in individuals with AUD with and without NUD.

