
Subjects will be reimbursed for the initial assessment visit (\$50) and for the MRI visit (\$100) as well as the result of one choice, chosen at random, during the scanner PDD task (average = \$55, this gift card may be given immediately or delayed up to one year and it may range from \$0 - \$140, depending on the random answer selected. During the task, subjects will choose whether they want \$20 now or a different amount at a later date- we will randomly select one of their answers). The third visit for cognitive battery will be an additional (\$50). Subjects who participate in follow ups (NAUD and AUD groups) will receive \$40 for each monthly visit and individuals receiving a second scan will be paid an additional \$100 and variable amount (average \$55, also may be delayed). Additionally, any enrolled subject who refers another individual will receive \$10 for each referral that participates in the first visit of the study. Some of these visits may be combined but reimbursement will remain the same. To avoid giving subjects cash, payment is provided in the form of widely accepted gift cards. **Comments:** As VA subjects are overwhelmingly male, special efforts will be made to recruit women, not only veterans, but from community detox and treatment programs. Gender is an important consideration and will be used as a covariate in all our analyses and gender effects will be specifically investigated in both Aims. We make special efforts to collect severity of use criteria, including age of onset, lifetime use and average daily use. We will use these variables as covariates and explore dependence of imaging measures on severity criteria.

Subjects may be contacted over the phone at two weeks after Visits 3, 4, and 5 so that we maintain contact and reduce drop out. Subjects will be asked to provide information kept in their study journals (see C3b2) including alcohol and cigarette use. If subjects are unable to make it to Visits 4, 5 or 6, these visits may be conducted over the phone and subjects will be paid at their next in-person appointment.

Appointment confirmation emails may be sent. They will be sent to participants using Azure. Brief scheduling correspondence may also happen through Azure if the study team is not able to connect with the subject via phone.

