A clinician will be available to consult with any participants who experience discomfort for any reason during the study visit. Subjects will be asked to remain in laboratory either until the problem has been resolved or immediate referral to appropriate treatment is accomplished. Subjects not in need of emergent treatment will be offered referral to counseling or other support resources as appropriate. Substance-dependent subjects (except control smokers) will all be in remission and undergoing residential treatment to ensure availability of counseling and support after study visits. The subject may request termination of the assessment at any time.

Subjects may refuse any single non-critical procedure in the study if it makes them uncomfortable without disqualification from the rest of the study.

C11. Participation of Non-Veterans: This is an ambitious study and requires recruitment of subjects who have been abstinent less than one month and one group of subjects who have AUD, but do not use nicotine. There are also significant gender effects which necessitate having a gender balanced sample. We will, therefore, need to recruit non-veterans to meet our ambitious recruitment goals, recruit sufficient women and subjects rare in the veteran treatment population. The [name] lab has established relationships with treatment programs within and outside the VA Portland HCS which will facilitate recruitment. Non-veterans will be recruited from community alcohol detox and treatment programs, through advertisement on OHSU's Study Participation Opportunities web page, and, if necessary for controls, Craig's List.

C12. Potential Benefits of Research to Subjects and Others

This project is not intended to benefit individual subjects but results may help us understand the neurobiology of alcohol and tobacco co-addiction and tailor treatment approaches to co-addicted individuals seeking treatment in the future.

C13. Importance of Knowledge to be Gained

The results of this project will be valuable for planning treatment options for dually addicted individuals by [name]

predicting and evaluating treatment response using neuroimaging. A predictive model will help individualize relapse risk through a better understanding of neurobiological factors that influence addiction, craving and cognition.

C14. Data and Safety Monitoring Plans

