Serum, leukocytes (from whole blood samples) and a buccal swab will be obtained (via separate permission on the HIPAA and ICF), linked to study data for coded storage in the MARC Translational Service Core Biorepository ([name], Administrator). No PHI will be stored in the data repository and repository data will be coded by an identifier (NAUDXXX), where XXX is a pseudorandom number. The code for the repository identifier will be identical to the study identifier and there will be a single spreadsheet linking to identifiable information that will be destroyed or encrypted at the closure of this study. Information collected for the contact repository will be stored on a password protected spreadsheet separate from the coded study data and will just have PHI and contact information.

C16. Oversight

IRB-approved study staff will ensure that any protocol deviations or adverse event will be reported immediately to the PI, who will examine the patient and determine if any additional evaluation or treatment is needed. The PI will ensure that significant adverse events are properly reported to the IRB (within 5 days to comply with VA policy). The [name] Lab will examine all cumulative adverse events semi-annually to determine if there are any systematic problems.

C17. Inclusion/Vulnerable Populations

Women and Minorities: Given that gender effects may be prominent in this population, it is important that the ratio of male/female subjects approach 50/50. We will recruit outside of the VA SATP to ensure that women are represented equally with men, in alcohol detox and treatment centers in the Portland area. Minority subjects will be recruited to be a representative cross section of the Portland, Oregon population. That population is primarily Caucasian 82.4%, with 7% African-American, 7%, Asian, 1.8% Native Hawaiian or Other Pacific Islander, and 1.8% Native American. Additionally, the population will be primarily non-Hispanic 93%, with 7% Hispanic. Pregnant Women are excluded and must have a negative pregnancy test.

Children: Children will be excluded from this study.

Prisoners: No prisoners will be included. If subjects are incarcerated at the time of follow-up, they will be dropped from the study.

Decisionally Impaired: Decisionally impaired subjects will not be recruited or included in the study.

C18. Determining VA from Non-VA Research

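### Gender balance is targeted for the whole sample but not within the four compared groups, and the SVM and connectivity t-tests state no adjustment for gender

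*Combined protocol and SAP*

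**What the plan says.** - **Target.** C11 says: "There are also significant gender effects which necessitate having a gender balanced sample". C17 adds that "it is important that the ratio of male/female subjects approach 50/50". Both refer to the study population as a whole. Table 1 and the rest of C1 contain no gender quota, matching or stratification by group. The only stratified split in the plan (C6b) is by relapse status.
- **How balance is to be reached.** C1 (Comments): "As VA subjects are overwhelmingly male, special efforts will be made to recruit women, not only veterans, but from community detox and treatment programs". C17: "We will recruit outside of the VA SATP to ensure that women are represented equally with men".
- **Link between recruitment source and group.** The Specific Aims report that the Portland VA treatment program "finds that 90% of veterans treated for AUD also meet criteria for NUD". C11 turns to non-veterans both for enough women and for types of subject seldom seen among treated veterans, shortly after naming people with AUD who do not use nicotine.
- **Adjustment.** C1 (Comments) says that gender "will be used as a covariate in all our analyses and gender effects will be specifically investigated in both Aims".
- **Analyses.** C4 compares connectivity between groups with two-tailed t-tests and names no covariate. C7b and C7c (Randomise) name none either, whereas the cytokine regression in C2a does include sex. C6 lists demographic variables among the SVM inputs. C6a builds six pairwise classifiers, and C6c sets a balanced-accuracy benchmark of about 70%.

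**The concern.** The reason given for balance is that gender affects the measurements. In a study that compares groups, balance protects the comparisons only if it holds inside the groups. An overall 50/50 split can be met with very different male shares in NAUD and AUD.

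The stated recruitment facts point towards such a difference. The VA source is mostly male and mostly supplies drinkers who also smoke, while women and non-smoking drinkers are both to be sought elsewhere. Nothing in the plan would detect or correct a drift by group.

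The exposed comparison is NAUD versus AUD, which carries the co-addiction question. Hypothesis 2a expects the classifier to reveal neuroadaptations specific to co-addiction. If gender differs between the two groups and is available to the SVM, part of the separation may be due to gender and be read as neural.

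**Working it through.** **Inputs from the plan.** 200 subjects (C1) and 50 per group (C8); 4 × 50 = 200, which agrees. An overall 50/50 target (C17) means 100 men. Balanced accuracy is half the sum of sensitivity and specificity (C6c). The C8 power of 0.99 at 50 per group cannot be reproduced, because the pilot map and effect size are not given. Nothing below depends on it.

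**Assumed.** Male shares pN in NAUD and pA in AUD. The documents give neither, so a range is shown.

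**Step 1: can the overall target be met with unequal groups?** Yes.
- NAUD 35 men, AUD 15, NUD 25, CS 25: total 100 of 200.
- NAUD 35, AUD 25, NUD 20, CS 20: total 100 of 200.

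**Step 2: gender-only accuracy, NAUD versus AUD.** For the rule that calls men NAUD and women AUD, balanced accuracy = ½(pN + 1 − pA).

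**Step 3: cost of adjusting for gender.** With p = (pN + pA)/2, the group-gender correlation is φ = [(pN − pA)/2] / √[p(1 − p)]. The variance factor is 1/(1 − φ²) and the effective n per group is 50(1 − φ²). Example at 70%/50%: φ = 0.10/√0.24 = 0.204, so the factor is 1/(1 − 0.0417) = 1.04.

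| Male share NAUD/AUD | Men needed in NUD + CS (of 100) | Gender-only balanced accuracy | Variance factor | Effective n per group |
|---|---|---|---|---|
| 50%/50% | 50 | 50% | 1.00 | 50 |
| 60%/40% | 50 | 60% | 1.04 | 48.0 |
| 70%/50% | 40 | 60% | 1.04 | 47.9 |
| 80%/50% | 35 | 65% | 1.11 | 45.1 |
| 70%/30% | 50 | 70% | 1.19 | 42.0 |
| 90%/50% | 30 | 70% | 1.24 | 40.5 |
| 80%/20% | 50 | 80% | 1.56 | 32.0 |

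Reaching 70% therefore needs a gap of 40 percentage points. If both groups drew men at 50%, a gap that large in either direction would have a probability of about 0.00008. Only systematic differences in recruitment could produce it.

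**Step 4: gender-by-group effects.** The variance ratio is the sum of 1/(cell size) divided by 4/25. At 70%/30% it is (2/35 + 2/15)/0.16 = 1.19; at 80%/20% it is (2/40 + 2/10)/0.16 = 1.56.

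**Step 5: bias where gender is left out.** The bias in a mean contrast is the gap times the gender effect. For an assumed gender effect of 0.5 SD it is 0.20 × 0.5 = 0.10 SD at 70%/50% and 0.40 × 0.5 = 0.20 SD at 70%/30%. An additive covariate removes it.

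**Step 6: limits of the accuracy figures.**
- Four groups: a gender rule can name only one group for men and one for women, so mean recall is (largest male share + largest female share)/4. At 70/30/50/50 that is (0.7 + 0.7)/4 = 35%, and it can never exceed 2/4 = 50%.
- Three-month relapse: if gender acts only through group, male shares of 70%/30% with assumed relapse of 60% versus 40% give 54%. Reaching 70% at those shares needs relapse of 100% versus 0%.

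**The case against.** The strongest reply is that the plan already promises gender as a covariate in every analysis. This largely stands for regression-type contrasts with men and women in each group. A reader might infer that the NAUD-AUD contrast is confounded outright, but the documents do not support that: additive confounding is handled, and what remains is some lost precision and reliance on the model. The reply does not reach the SVM, where a demographic input is a predictor and not an adjustment. It also leaves open how the C4 t-tests would meet the promise.

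Second, the 70%/30% and 80%/20% splits are assumed mirror images. The documents support NAUD leaning male. They do not show AUD to be mostly female: community programs can supply women to either group, and veterans with AUD alone also come from a mostly male pool. This stands, and the 70%/50% row is the more moderate case.

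Third, a reader might infer that gender alone would meet the C6c benchmark. That requires a 40-point gap and applies only to the pairwise NAUD-AUD classifier. C6c does not say which classifier its benchmark covers, and C6 does not name gender among the demographic inputs.

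Fourth, a reader might infer that power would collapse. C8 concerns AUD versus CS and gives several anchors. C3c tests group differences in the task analysis on the a priori ROIs, for which C8 reports 0.99. Even from the whole-brain figure of 31 per group for 0.8 (two-sided α of 0.05 assumed), power goes from 0.94 at n = 50 to 0.90 at 42 and 0.81 at 32.

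Last, within-group targets create eight cells, and C11 already treats some subjects as rare. This is a fair argument for a soft range and against a hard quota.

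**Conclusion.** The concern holds in a limited form. The plan sets gender balance at a level that does not protect its group comparisons, and its own recruitment facts make a male-leaning NAUD group foreseeable. The imbalance is a risk, not a documented fact.

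For covariate-adjusted contrasts the cost is modest: a variance factor of 1.04 at 70%/50%, and 1.19 to 1.56 under the assumed mirror-image splits. The more serious exposure is interpretive. In the NAUD-AUD classifier, gender alone could supply 60% balanced accuracy at 70%/50%, or 70% at 70%/30%, and the plan reports nothing that would separate this from a neural signal. The C4 t-tests, as written, make no adjustment at all.

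These sizes rest on 50 subjects per group, the assumed male shares, and gender being among the demographic inputs.

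**What to change.** 1. **C11 and C17:** state the gender target within each group as a soft range, for example 40-60% women, at least for AUD and NAUD. Keep a tally by group and steer recruitment to match. At 25/25 in each group, gender-only accuracy is 50%, the variance factor is 1.00 and the total stays at 200.
2. **C4:** replace the t-tests by a linear model with group and gender, as C1 promises. Naming gender in the C7b and C7c contrasts would settle the same question there.
3. **C6a and C6c:** report a gender-only (or demographics-only) classifier beside each pairwise accuracy, and claim neural separation only for accuracy beyond it. Say which classifier the 70% benchmark applies to.

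Residualising features on gender is an optional modelling choice and is not needed for this point.

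**Cost:** protocol wording, a recruitment tally and a few lines of code, with no extra subjects or procedures. The real downside is that scarce gender-by-group cells may fill more slowly. The documents give no figures from which to estimate the delay.
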